The maximum duration of participation is expected to be 112 weeks as follows:

- Planned duration of screening period: up to 42 days
- Planned duration of treatment period (baseline visit to end of treatment visit): up to 104 weeks
- Planned duration of safety follow-up period: 14 days (-4 days/+7 days).

Statistical analysis:

Endpoints and statistical analysis:

Subject Populations

- The **intent-to-treat (ITT) set** (those subjects who are considered enrolled in the study) will include all subjects who sign informed consent form and are eligible for the study based on the defined inclusion/exclusion criteria. There is a possibility that a subject is enrolled in the study but does not receive a dose of investigational product
- The **modified intent-to-treat (mITT) set** will include all enrolled subjects (all subjects from the ITT) who have received at least 1 dose of investigational product and completed at least 1 efficacy assessment of the endpoints being analyzed.
- The **safety set** will include all subjects in the ITT set who receive at least 1 dose of investigational product. The safety set will be used for the analysis of safety endpoints.
- The **per-protocol (PP) set** will include all subjects in the ITT excluding subjects with major protocol deviations. The PP set will be identified by a team consisting of, at a minimum, a physician and a statistician from Shire.
- The **completers set** will include all subjects in the TTT who have valid values of primary efficacy endpoints (eGFR and LVMI) for both baseline and Week 104 assessments.

Primary Efficacy Endpoints:

The primary efficacy endpoints are:

- Change from baseline at Week 104 in renal function, assessed by eGFR (using the CKD-EPI formula)
- Change from baseline at Week 104 in cardiac structure, assessed by LVMI using cMRI.

Secondary Efficacy Endpoints:

The secondary efficacy endpoints are:

- Annualized rate of change in eGFR
- Annualized rate of change in LVMI
- Change over time in eGFR
- Change over time in LVMI
- Change over time in proteinuria, measured by PCR
- Change over time of the number of fibrotic segments suggestive of cardiac fibrosis as assessed by volume of fibrosis, measured by cMRI
- Change over time in interventricular septal end-diastolic thickness and posterior wall thickness in diastole, measured by cMRI
- Change over time in plasma globotriaosylsphingosine (lyso-Gb3).

Exploratory Efficacy Endpoints:

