4.4 Duration of Subject Participation and Study Completion Definition

A subject's maximum duration of participation is approximately 112 weeks. This includes the screening period (up to 42 days), the treatment period (104 weeks), and the safety follow-up period (14 days [-4 days/+7 days] from the end of treatment [EOT] infusion, or the last infusion for subjects who withdraw early from the study). A subject is considered enrolled in the study when he or she signs informed consent and passes the inclusion/exclusion criteria.

The overall planned study duration is approximately 6 years. The first subject is expected to be enrolled in 2022. The Study Completion Date is defined as the date on which the last subject in the study completes the final protocol-defined assessment(s). This includes the follow-up visit or contact, whichever is later (refer to Section 8.1.4 for the defined follow-up period for this protocol).

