8.1.2 Baseline Period (Day 7 to Day 0/Week 0)

All baseline assessments and procedures are to be performed at the clinical site. The baseline assessments may be completed over a period of 7 days as long as all baseline assessments and procedures are completed prior to the first REPLAGAL infusion. The day of the first REPLAGAL infusion is considered Day 0/Week 0 and all future study visits and windows should be timed from the first infusion.

Baseline assessments and procedures are outlined in Table 1 and listed below:

- Review of inclusion/exclusion criteria
- Administer urine pregnancy test (for women of childbearing potential only). The urine pregnancy test should be administered by the clinical site before any other procedures are completed. If the urine test is positive, a blood sample will be collected for serum β-hCG testing and sent to the central laboratory for analysis.
- Measure weight
- Perform 12-lead ECG

CONFIDENTIAL

Shire SHP675-301 Protocol Amendment 6 **REPLAGAL**[®] (agalsidase alfa)

17 Feb 2022

- Collect blood samples to perform serum chemistry (sodium [Na+], potassium [K+], chloride [Cl-], bicarbonate [HCO3-], calcium [Ca2+], magnesium [Mg2+], phosphate, creatinine, urea nitrogen [BUN], glucose, albumin, bilirubin, alkaline phosphatase, alanine aminotransferase [ALT], aspartate aminotransferase [AST], triglycerides, cholesterol, LDL cholesterol, HDL cholesterol, and hematology (complete blood count: hematocrit [Hct]; hemoglobin [Hb]; RBC; WBC; platelets; basophils; basophils/total cells; eosinophils; eosinophils/total cells; immature granulocytes; lymphocytes; lymphocytes/total cells; monocytes; monocytes/total cells: neutrophils: and neutrophils/total cells) laboratory tests
- eGFR (to be calculated by a Shire-designated laboratory; if the eGFR measurement at ٠ screening is not within the range, a second eGFR measurement may be completed and, if in range, used as the screening value. If a second measurement is taken, a minimum of 1 week and maximum of 30 days should separate it from the first.
- Collect blood samples for ADA testing ٠
- Collect blood samples for evaluation of plasma lyso-Gb3 levels •
- Collect blood samples for assessments of levels of inflammatory biomarkers •
- Collect urine samples for urinalysis •
- Administer the following questionnaires: SF-36v2 BPI-SF PGI-S BFI GSRS Record AEs ٠
- Record AEs •
- Review of prior and concomitant medications, therapies, and medical/surgical • interventions

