8.2.1.2 Confirmation of Study Eligibility

At screening, each subject will be reviewed for eligibility against the study inclusion/exclusion criteria. Subjects who do not meet the study entrance criteria will not be allowed to participate in the study, and the reason(s) for the subject's ineligibility will be documented; the subject will be considered a screen failure. If the eGFR measurement at screening is not within the range, a second eGFR measurement may be completed and, if in the stipulated range, used as the screening value. If a second measurement is taken, a minimum of 1 week and maximum of 30 days should separate it from the first measurement.

Subject eligibility will be confirmed at baseline on the basis of review of the study entrance criteria. Subjects should not be administered study medication unless they continue to meet all inclusion/exclusion criteria at the time of dosing. For any subjects who do not continue to meet the study entrance criteria, the reason(s) for the subject's ineligibility for the study will be documented and the subject will be considered a screen failure.

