In a recently completed Shire-sponsored study (HGT-REP-081) with REPLAGAL, 27 of 167 enrolled subjects discontinued from the study, representing a drop-out rate of 16%. Two other recently published studies, ATTRACT and FACETS, provide recent discontinuation data in patients with Fabry disease. In ATTRACT (Hughes et al. 2017), a 9% drop-out rate was observed at 18 months, but a much higher rate of 16% was reported in patients who entered the 12-month open-label extension. In FACETS (Germain et al. 2016), a 20% drop-out rate was noted among migalastat-randomized patients after 24 months of treatment. Although not specific to Fabry disease, a review (Wood et al. 2004) of 71 randomized clinical studies published in leading medical journals found that 18% of the studies had a drop-out rate of 20% or higher (ie, studies published in specialist journals show that the drop-out rate is likely to be higher).

It is anticipated that the majority of subjects who do not meet the criteria to be considered as part of the completers set will have data that can be meaningful for analysis. Enrolled subjects who have received at least 1 dose of investigational product and who have completed at least 1 efficacy assessment of the endpoints being analyzed will be part of the modified intent-to-treat (mITT) set (see Section 9.4). The mITT set will be used for all analyses related to primary efficacy, secondary efficacy, inflammatory biomarker, and PRO endpoints. The study population will target approximately 40% females and 40% males for enrollment.

9.4 **Statistical Analysis Sets**

The statistical analysis will include the following analysis sets:

- The intent-to-treat (ITT) set (those subjects who are considered enrolled in the • study) will include all subjects who sign informed consent form and are eligible for the study based on the defined inclusion exclusion criteria. There is a possibility that a subject is enrolled in the study but does not receive a dose of investigational product.
- The modified intent-to-treat (mITT) set will include all enrolled subjects (all subjects from the ITT) who have received at least 1 dose of investigational product and completed at least 1 efficacy assessment of the endpoints being analyzed.
- The safety set will include all subjects in the ITT set who receive at least 1 dose of • investigational product. The safety set will be used for the analysis of safety endpoints.

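### The safety set is nested in an eligibility-restricted ITT set, so a subject dosed in breach of an entry criterion can be left out of the safety tables

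*Combined protocol and SAP*

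**What the plan says.** Three definitions combine, and the synopsis (Subject Populations) and Section 9.4 agree on them.

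- **ITT set.** It "will include all subjects who sign informed consent form and are eligible for the study based on the defined inclusion/exclusion criteria". The same bullet equates these subjects with those considered enrolled. Section 4.4 says when that happens: "A subject is considered enrolled in the study when he or she signs informed consent and passes the inclusion/exclusion criteria".
- **Safety set.** It is drawn from ITT. In the synopsis it "will include all subjects in the ITT set who receive at least 1 dose of investigational product". In Section 9.4: "The safety set will include all subjects in the ITT set who receive at least 1 dose of" investigational product. Section 9.6 and the synopsis base every safety analysis on this set.
- **Other sets.** The mITT set "will include all enrolled subjects (all subjects from the ITT) who have received at least 1 dose of investigational product" and has at least one efficacy assessment. The per-protocol and completers sets are also subsets of ITT.

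Section 7.1 reserves the term screen failure for consented subjects who fail the criteria and have not been dosed. Section 8.2.1.2 says a subject should not be dosed unless he or she still meets all "inclusion/exclusion criteria at the time of dosing". Section 8.1.3 starts the treatment period only once continued eligibility has been confirmed. No section says how to analyse a subject who is dosed despite a breach.

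**The concern.** A safety set normally answers one question: who was exposed? Here membership also depends on eligibility, through ITT. If an entry safeguard fails and the subject is infused, the definitions can remove that subject from the tables because the safeguard failed.

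This could happen in practice. Several exclusions in Section 5.2 rest on history, such as prior chloroquine, amiodarone or gentamicin, or a relevant hypersensitivity history, and history can come to light late. If a hypersensitivity history emerged only after an infusion-related reaction and the subject was then judged ineligible, a literal programmer would drop that reaction from the summaries. Section 2.2 describes infusion-related reactions as the most common adverse reactions to this product.

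What is at stake is the completeness of the safety summaries in a trial of about 45 subjects. Data collection and expedited reporting are not affected.

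**Working it through.** The main check is a trace of set membership, followed by a short illustration of size.

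**Membership of a dosed subject who breaches a criterion**

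| Case | Screen failure (7.1)? | In ITT? | In safety set? |
|---|---|---|---|
| Dosed without passing the eligibility check | No, because dosed | No: not eligible, and not enrolled under 4.4 | No, on any reading |
| Passed the check, dosed, breach found later; ITT read literally (the subject is not in fact eligible) | No, because dosed | No | No |
| Same subject; ITT read through 4.4 (the subject passed at enrolment) | No, because dosed | Yes | Yes |

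In the first two rows the mITT, per-protocol and completers sets give no way back, since each is a subset of ITT. Section 8.2.1.2 also calls a subject who no longer qualifies at baseline a screen failure. That sentence belongs to the pre-dose check and does not place a dosed subject in any analysis set.

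**Size**

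The plan's enrolment figure reproduces: 36 / (1 − 0.20) = 45. The documents give no rate of dosing in breach, so the counts below are assumptions. Take 45 dosed subjects, of whom k breach a criterion and are dropped.

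| k (assumed) | Share of exposed subjects missing | Left in safety set | Upper 95% bound if no events, 1 − 0.05^(1/n) |
|---|---|---|---|
| 0 | 0% | 45 | 6.4% |
| 1 | 1/45 = 2.2% | 44 | 6.6% |
| 2 | 2/45 = 4.4% | 43 | 6.7% |
| 3 | 3/45 = 6.7% | 42 | 6.9% |

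The loss of precision is trivial. The content of the tables can change more: if the dropped subject had the only occurrence of an event, the reported incidence goes from 1/45 = 2.2% to 0/44 = 0%.

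**Effect on the primary analysis under the literal reading**

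The planned effect sizes are (6 − 1.7)/7 = 0.614 for eGFR and (10 − 0.64)/15 = 0.624 for LVMI. With a one-sample t-test, one-sided 0.0125 and n = 36, noncentral-t power is 90.5% and 91.4%, in line with the stated figure of at least 90%. If one breach came out of the 36 evaluable subjects, power at n = 35 would be 89.6% and 90.5%. With three (n = 33) it would be 87.4% and 88.5%. That is about one percentage point per subject.

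**The case against.** The best defence is that ITT is tied to enrolment, and Section 4.4 describes enrolment as a status gained when the subject passes the criteria. Nothing says a later finding revokes it. On that reading, a subject who passed the check, was dosed and was later found in breach stays in both ITT and the safety set, and leaves only the per-protocol set if the deviation is major. This is a reasonable reading and probably the intended one. It is not stated, and it does not help a subject dosed without passing the check.

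Two stronger claims are tempting, and the documents do not support them.

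- A reader might infer that the primary ITT analysis works like a per-protocol analysis, with eligibility open to re-judgement after outcomes are known. No section provides for such re-judgement. The only set assembled by a review team is the per-protocol set. What remains is ambiguous wording.
- A reader might infer that the schedule builds in dosing before eligibility results are back, since Section 8.1.2 asks only that "all baseline assessments and procedures are completed prior to the first REPLAGAL infusion". Section 8.1.3 adds that continued eligibility must be confirmed before treatment begins. Dosing without that confirmation would be a deviation. It is also unclear whether a Day 0 eGFR outside the range would override a qualifying screening value, because inclusion criterion 8 is written around the screening measurement.

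It is also true that Appendices 3.2 and 3.5 keep adverse events collected from consent and SAEs reported within 24 hours regardless of relationship, so the gap is confined to analysis. Sections 9.1 and 9.5.3 leave detailed definitions to the SAP. But the safety-set rule is already written, so this is a rule to correct and cannot be treated as detail still to come.

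**Conclusion.** The point holds for the safety set. As written, a subject dosed without passing the eligibility check is in no analysis set, and a subject whose breach is found after dosing is in none if the ITT wording is taken literally. Two programmers could build different safety sets from the same text in the second case.

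The expected number is small, because such dosing is a protocol deviation. Each case would be 2.2% of 45 exposed subjects, on the assumption that 45 are dosed. The count itself is unknown. For ITT the finding is only that the wording should be made explicit. It does not threaten the primary comparison, and the effect on power would be about one point per subject lost from 36. The correction is worth making because exposed subjects should appear in the safety tables and the change costs almost nothing.

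**What to change.** In the synopsis, Section 9.4 and the SAP:

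1. **Safety set (main change).** Define it as all subjects who receive any amount of investigational product, with no reference to ITT or eligibility. The safety set need not then be a subset of ITT, and the disposition table should list any subject who is in one and not the other.
2. **ITT set (clarification).** State that membership is fixed when the subject passes the eligibility check at enrolment, consistent with Section 4.4, and is not revoked by a violation found later. Such violations are handled in the per-protocol set only.

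The cost is two reworded definitions, with no added visits, samples or data collection. A few subjects later found ineligible may stay in the primary analysis. The planned per-protocol analysis shows whether they matter.

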REPLAGAL (agalsidase alfa) will be administered at the globally approved dose of 0.2 mg/kg EOW by intravenous (IV) infusion over 40 minutes (± 10 minutes).

Methodology:

This is a global, Phase 3, multicenter, nonrandomized, open-label, single-arm, baseline-controlled study.

Eligible participants will be male and female adult subjects who are treatment naïve and who have a confirmed diagnosis of Fabry disease with left ventricular hypertrophy. Subjects with or without renal involvement may qualify for the study if their eGFR is 45 to 120 mL/min/1.73 m², as calculated by the Chronic Kidney Disease-Epidemiology (CKD-EPI) formula.

The study will include 1 arm, comprising subjects prospectively treated with REPLAGAL for up to 104 weeks. The change from baseline to Week 104 in eGFR and LVMI will be compared with reference values of patients with Fabry disease from the published literature (Schiffmann et al., 2009; Kampmann et al., 2008) who had similar baseline demographic and disease characteristics to the study subjects (Schiffmann et al., 2009) and who remained untreated for 2 years.

It is anticipated that at least 45 adult subjects with Fabry disease will need to be enrolled in order to obtain 36 evaluable subjects. To be considered evaluable, a subject must not have discontinued from investigational product and must have valid, nonmissing values of the primary efficacy endpoints (eGFR and LVMI) for both baseline and Week 104.

Potential subjects will participate in a screening period, which can last up to 42 days, to determine eligibility. After completion of baseline procedures and assessments, eligible subjects will receive 0.2 mg/kg REPLAGAL by IV infusion over 40 minutes EOW for 104 weeks and will have site visits approximately every 12 to 14 weeks during the 104-week treatment period. Subjects who discontinue from study treatment will continue to have study visits if they consent to do so. Approximately 14 days (-4 days/+7 days) after the last infusion or study visit, a safety follow-up contact or visit will occur to confirm the subject's safety.

Inclusion and Exclusion Criteria:

Inclusion Criteria:

The subject will not be considered eligible for the study without meeting all of the criteria below:

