The primary analysis for change from baseline at Week 104 in eGFR will be based on a mixed-effects model for repeated measures (MMRM) with multiple imputation under the assumption that the missing is not at random (MNAR) using the ITT population. A Bonferroni adjustment will be used to control the overall one-sided type I error rate of 0.025 for two primary endpoints. The primary null hypothesis to be tested for eGFR is that the mean change from baseline in eGFR at Week 104 of treated subjects will be less than or equal to -6 mL/min/1.73 m², the reference value from untreated subjects. The alternative hypothesis is that the mean change in eGFR is greater than -6 mL/min/1.73 m², the reference value of untreated subjects. A one-sided p-value to test if the mean change is greater than -6 mL/min/1.73 m² from MMRM model will be used to interpret that there is sufficient evidence to reject the null hypothesis. The model will include visit as the fixed effect; with adjustment for sex (male versus female), age at baseline and baseline eGFR. In the model, visit will be treated as a class variable, assuming an unstructured covariance matrix to model the within subject variability.

The primary analysis for change from baseline at Week 104 in LVMI will be based on a MMRM with imputation under the assumption that the missing is not at random using the ITT population. The primary null hypothesis to be tested for LVMI is that the mean change from baseline in LVMI at Week 104 of treated subjects will be greater than or equal to 10 g/m^{2.7}, the reference value from untreated subjects. The alternative hypothesis is that the mean change in LVMI is less than 10 g/m^{2.7}, the reference value of untreated subjects. A one-sided p-value to test if the mean change is less than 10 g/m^{2.7} from MMRM model will be used to interpret that there is sufficient evidence to reject the null hypothesis. The model will include visit as the fixed effect; with adjustment for sex (male versus female), age at baseline and baseline LVMI. In the model, visit will be treated as a class variable, assuming an unstructured covariance matrix to model the within subject variability.

Missing eGFR and LVMI data due to intercurrent event or other reasons will be handled according to the treatment policy strategy.

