Treatment policy strategy is defined as the strategy that considers "The occurrence of the intercurrent event is irrelevant: the value for the variable of interest is used regardless of whether or not the intercurrent event occurs." (per ICH E9 R1 Addendum). Intercurrent events can include but are not limited to the following: (1) discontinuation of study drug, (2) discontinuation of the study, or (3) initiation of a new treatment. In a situation that missingness of the eGFR or LVMI data cannot be predicted solely based on subject's observed data, such missingness will not be considered as missing at random, but rather as MNAR. The missing pattern will be evaluated and subjects with and without missing data will be compared to gain understanding of the nature of the missingness. Pattern-mixture models and Monte Carlo Markov Chain methodology will be implemented in

multiple imputation with a list of observed variables and covariates to impute missing eGFR and LVMI data with the assumption of MNAR. The covariates can be variables related to missingness identified in the comparison of subjects with and without missing data, the covariate can also be variables related to eGFR or LVMI based on medical input.

The analyses of the primary endpoints will be performed with all available data through Week 104. The repeated measure analyses will be based on the restricted maximum likelihood method assuming an unstructured covariance matrix to model the within-subject errors. If the analysis fails to converge, a compound symmetry covariance structure will be used to model the within-subject errors. Denominator degrees of freedom for the F test for fixed effects will be estimated using the Kenward-Roger approximation.

The following analyses will be performed for the primary endpoints to evaluate the robustness of the results from the primary analysis methods:

- MMRM analysis using the completers set
- MMRM analysis using the PP set.
- The eGFR and LVMI annualized rate of change and 95% CI will be estimated for subjects using the random intercept and slope model. Baseline eGFR or baseline LVMI, age at baseline, sex, and treatment duration on investigational product in year will be included in the model.
- Tipping point analysis with multiple imputation approach in ITT and mITT sets.

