The Bonferroni adjustment to control the type I error rate for the 2 primary endpoints is incorporated in the sample size determination. The Bonferroni adjustment does not make any assumptions of the primary endpoints.

For eGFR, with 36 evaluable subjects, the study has at least 90% power to detect a decrease after 104 weeks of treatment of -1.7 mL/min/1.73 m² compared with a reference untreated change of -6 mL/min/1.73 with SD=7 (effect size of 0.61) using a 1-sided one sample t-test at significance level of 0.0125. For LVMI, with

36 evaluable subjects, the study has at least 90% power to detect an increase after 104 weeks of treatment of 0.64 g/m^{2.7} compared with a reference untreated change of 10 g/m^{2.7} with SD=15 (effect size of 0.62) using a 1-sided one sample t-test at significance level of 0.0125.

It is anticipated that 45 subjects will need to be enrolled in the study in order to obtain 36 evaluable subjects, ie, subjects who have not discontinued from investigational product and who have valid, nonmissing values of primary efficacy endpoints (eGFR and LVMI) for baseline and Week 104 assessments (completers set).

FornoncommercialuseonW

Page 20

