- The **per-protocol (PP)** set will include all subjects in the ITT excluding subjects with ٠ major protocol deviations. The PP set will be identified by a team consisting of, at a minimum, a physician and a statistician from Shire.
- The **completers set** will include all subjects in the ITT who have valid, values of primary • efficacy endpoints (eGFR and LVMI) for both baseline and Week 104 assessments.

9.5 **Efficacy Analyses**

Primary Efficacy Endpoint 9.5.1

The primary efficacy endpoints are

- Change from baseline at Week 104 in renal function, assessed by eGFR (using the CKD-EPI formula)
- Change from baseline at Week 104 in cardiac structure, assessed by LVMI using cMRI.

The primary analysis for change from baseline at Week 104 in eGFR will be based on a mixed-effects model for repeated measures (MMRM) with multiple imputation under the assumption missing is not at random using the ITT population. A Bonferroni adjustment will be used to control the overall one-sided type I error rate of 0.025 for 2 primary endpoints. The primary null hypothesis to be tested for eGFR is that the mean change from baseline in eGFR at Week 104 of treated subjects is less than or equal to $-6 \text{ mL/min}/1.73 \text{ m}^2$, the mean change of reference untreated subjects. The alternative hypothesis is that the mean change in eGFR is greater than -6 mL/min/1.73 m², the mean change of the reference untreated subjects. A one-sided p-value to test if the mean change is greater than -6 mL/min/1.73 m² from MMRM model will be used to interpret that there is sufficient evidence to reject the null hypothesis. The model will include visit as the fixed effect; with adjustment for sex (male versus female), age at

Shire SHP675-301 Protocol Amendment 6 REPLAGAL[®] (agalsidase alfa)

baseline and baseline eGFR. In the model, visit will be treated as a class variable, assuming an unstructured covariance matrix to model the within subject variability.

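### The completers-set MMRM, one of four robustness analyses, drops a subject with complete data on one primary endpoint only because the other endpoint is missing at Week 104

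*Combined protocol and SAP*

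**What the plan says.** **Definition.** The Subject Populations part of the synopsis defines one completers set: enrolled subjects with "valid values of primary efficacy endpoints (eGFR and LVMI) for both baseline and Week 104 assessments". Section 9.4 repeats the condition ("efficacy endpoints (eGFR and LVMI) for both baseline and Week 104 assessments"). No separate eGFR or LVMI completers set is defined.

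**Use.** The synopsis opens its list of robustness analyses for the primary endpoints with "MMRM analysis using the completers set", and Section 9.5.1 does the same. Both lists then give an MMRM in the per-protocol set, a random intercept and slope model, and a tipping-point analysis.

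**Primary analysis.** Each endpoint has its own hypothesis and its own MMRM. The eGFR model is run "with multiple imputation under the assumption that the missing is not at random (MNAR) using the ITT population", and the LVMI model also uses the ITT population with imputation. On multiplicity the synopsis says: "A Bonferroni adjustment will be used to control the overall one-sided type I error rate of 0.025 for two primary endpoints". Power is computed for each endpoint "using a 1-sided one sample t-test at significance level of 0.0125".

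**Related definitions.** The mITT set is tied to the endpoint in hand: the subject must have been dosed and have "completed at least 1 efficacy assessment of the endpoints being analyzed". An evaluable subject, used for sizing, must not have discontinued investigational product and "must have valid, nonmissing values of the primary efficacy endpoints (eGFR and LVMI) for both baseline and Week 104". The synopsis (Number of subjects and Sample Size Justification) labels these evaluable subjects the completers set, and Section 9.3 attaches the same label to the 20% non-completion figure.

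**The concern.** A completers analysis of eGFR asks whether the result holds among subjects whose eGFR was observed to the end. Here membership also depends on a different measurement. eGFR comes from serum creatinine (Section 8.2.2.2). LVMI comes from cMRI read by a central reader (Section 8.2.2.1), and the Week 104 scan may fall up to 14 days either side of the infusion day (Table 1, footnote c). One can be missing or invalid without the other.

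The endpoints do not depend on each other for inference, since each is tested at its own one-sided 0.0125. The documents give no reason for filtering one endpoint's check by the availability of the other. What is at stake is the precision of one supportive analysis per endpoint and, if missingness on one endpoint is related to outcome on the other, its estimate. Section 9.8 itself warns that losing data from 45 subjects is costly.

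**Working it through.** **1. The plan's own figures.** One-sample t-test, one-sided 0.0125, n = 36, power from the noncentral t distribution:

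- eGFR: effect size (−1.7 − (−6))/7 = 4.3/7 = 0.614; power 90.5%.
- LVMI: effect size (10 − 0.64)/15 = 9.36/15 = 0.624; power 91.4%.
- Enrolment: 36/(1 − 0.20) = 45.

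All three agree with the synopsis and Section 9.3. The joint condition does no harm in the sizing.

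**2. How many subjects the joint rule can remove.** Planned non-completers: 45 − 36 = 9. Split them as a (Week 104 eGFR but no valid scan), b (valid scan but no Week 104 eGFR) and c (outside the set for any other reason), with a + b + c = 9. The documents give only the total. So a and b each lie between 0 and 9, and they cannot both be 9. Baseline LVMI should rarely be the gap, because inclusion criterion 9 requires a screening scan and that scan serves as baseline.

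**3. What an endpoint-specific set would hold.** Let k be a for the eGFR analysis or b for the LVMI analysis. The endpoint-specific set has 36 + k subjects, the joint rule drops k/(36 + k) of them, and the SE of a simple mean is SD/√(36 + k). Values of k are assumptions across the possible range.

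| k | n | share dropped | eGFR SE (SD 7) | eGFR power | LVMI SE (SD 15) | LVMI power |
|---|---|---|---|---|---|---|
| 0 | 36 | 0% | 1.17 | 90.5% | 2.50 | 91.4% |
| 2 | 38 | 5% | 1.14 | 92.1% | 2.43 | 93.0% |
| 4 | 40 | 10% | 1.11 | 93.5% | 2.37 | 94.2% |
| 9 | 45 | 20% | 1.04 | 96.1% | 2.24 | 96.6% |

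Power here describes the supportive analysis only, using the simple t-test of the sample-size section.

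**4. Repeated values lost.** Table 1 schedules eGFR at eight post-baseline visits (Weeks 12, 26, 40, 52, 64, 78, 92, 104) and cMRI at two (Weeks 52, 104). A subject missing only the Week 104 scan takes up to eight eGFR values out of the eGFR completers MMRM. A subject missing only Week 104 eGFR takes up to two LVMI values out of the LVMI one.

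**5. Effect on the estimate (hypothetical).** For simple means, adding the k subjects shifts the estimate by k/(36 + k) × (their mean − the mean of the 36). Take k = 4 for eGFR, with the 36 at the planned −1.7:

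- The four at −6, the untreated reference: (36 × (−1.7) + 4 × (−6))/40 = −2.13. The joint set looks better by 0.43, which is 0.43/1.17 = 0.37 SE.
- The four at 0: (36 × (−1.7) + 4 × 0)/40 = −1.53. The joint set looks worse by 0.17.

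The LVMI counterpart of the first case (four at +10, 36 at +0.64) gives 63.04/40 = 1.58, a shift of 0.94, or 0.94/2.50 = 0.37 SE.

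Even in the first eGFR case the completers conclusion stands. The distance from −6 is 4.3/1.167 = 3.7 SE in the joint set and 3.87/1.107 = 3.5 SE in the eGFR-specific set, against a critical value of about 2.3.

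**The case against.** The strongest reply is that a single complete-case population is a legitimate choice. It shows the renal and cardiac results in the same patients, and it matches the evaluable subjects who size the trial. The mITT wording is a weak precedent, because that set also serves secondary, biomarker and patient-reported endpoints and so needs general wording. The number affected is also probably small: the 20% rests on study drop-out rates (Section 9.3), drop-outs usually lose both measurements, and Section 7.3 keeps subjects who stopped treatment out of the completers set even if they attend Week 104.

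Much of this stands. It limits the size of the point and rules out any claim against the sample size. The common-population argument, however, is not one the documents make, and the joint table could still be shown beside endpoint-specific ones.

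A reader might infer three stronger things that the documents do not support:

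- *That the robustness assessment as a whole is compromised.* The per-protocol, random-slope and tipping-point analyses carry no both-endpoints condition.
- *That observed Week 104 data are thrown away.* They are left out of one supportive analysis. The primary analysis uses all available data through Week 104.
- *That the rule favours the drug.* Nothing in the documents links a missing scan to faster eGFR decline, or a missing creatinine to LVMI growth.

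**Conclusion.** The point holds as a minor one. For each primary endpoint, the completers MMRM excludes subjects with complete data on that endpoint when the other is missing at baseline or Week 104, and no reason is given. The number excluded cannot be derived from the documents: it is 0 to 9 of 45, assuming the planned 20% non-completion is met exactly. At the extreme, one endpoint's completers analysis loses 20% of its subjects and its power falls by 5.6 points for eGFR (96.1% − 90.5%) or 5.2 for LVMI (96.6% − 91.4%). The 0.43 shift in mean eGFR change is an illustration with assumed inputs, and its sign could be reversed. The ITT primary tests, their type I error and the planned 36 from 45 do not change.

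The same definition has a second problem. The synopsis (Number of subjects and Sample Size Justification) and Section 7.3 keep subjects who discontinued investigational product out of the completers set; the formal definitions in the synopsis and Section 9.4 contain no such condition. These passages must be reconciled, and doing so would not remove the both-endpoints issue.

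**What to change.** 1. In the synopsis (Subject Populations) and Section 9.4, define the completers set for each robustness MMRM as enrolled subjects with valid baseline and Week 104 values of the endpoint under analysis. Run the eGFR model in eGFR completers and the LVMI model in LVMI completers.
2. Keep the both-endpoints condition for the sample-size count only, under the separate name evaluable subjects. Replace the completers-set label in the synopsis (Number of subjects and Sample Size Justification) and in Section 9.3 to match. If only the two definitions were edited, one label would denote two different sets.
3. In the same edit, state once whether discontinuing investigational product removes a subject from the set, and align the synopsis and Sections 7.3, 9.3 and 9.4.

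The cost is a few sentences of text and two completers tables whose n may differ slightly. No new data, change of sample size or change to the primary analysis is needed.
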